8.1.6 Safety Analyses

All safety analyses will be performed on the safety data set unless otherwise specified. Comparisons between each ABBV-8E12 dose group and placebo will be performed with two-sided test at the significance level of 0.050, if applicable. All safety assessments that are taken no more than 20 weeks after the last dose of study drug administration will be included in the safety evaluation of the Double-blind Treatment Period, and all safety assessments that are taken more than 20 weeks after the last dose of study drug will be included in the safety evaluation for the Post-treatment Follow-up Period.

Study Drug Exposure and Compliance

The number of doses on study drug will be summarized by treatment group and all treatment groups combined. The number and percentage of subjects with at least 90% compliance with study drug dosing will be summarized by treatment group and all treatment groups combined.

Adverse Events

A treatment-emergent adverse event (TEAE) is defined as any adverse event that begins or worsens in severity on or after the first study drug dose date and no more than 20 weeks after the last study drug dose date.

All other safety assessments that are taken no more than 20 weeks after the last dose of study drug will be included in the safety evaluation of the Double-blind Treatment Period, and all safety assessments that are taken more than 20 weeks after the last dose of study drug will be included in the safety evaluation for the Post-treatment Follow-up Period.

Unless otherwise specified, treatment group differences in continuous safety variables (e.g., change from baseline to final observation on laboratory tests) will be assessed using an ANOVA model with treatment as the main effect, and the treatment group differences in binary safety variables will be evaluated using Fisher's exact test.

8.1.6.1 Analysis of Adverse Events

Adverse events will be coded using the most current version of the Medical Dictionary for Regulatory Activities (MedDRA). The number and percentage of subjects who report TEAEs will be tabulated by MedDRA system organ class (SOC) and preferred term for each treatment group, overall ABBV-8E12 and all treatment groups combined. Treatment group differences between each ABBV-8E12 dose group and the placebo group will be analyzed using Fisher's exact test.

The number and percent of subjects experiencing treatment-emergent SAEs (including deaths) and adverse events leading to premature discontinuation of study drug will be tabulated by MedDRA SOC and preferred term for each treatment group, overall ABBV-8E12 dose groups, and all treatment groups combined. Treatment group differences between each ABBV-8E12 dose groups and placebo will be analyzed using Fisher's exact test.

8.1.6.2 Analysis of Laboratory Tests

Change from baseline to each double-blind visit value and to the minimum, maximum and final double-blind value will be presented for each continuous hematology, chemistry and urinalysis parameters. Treatment differences between each ABBV-8E12 dose group and placebo in change from baseline to minimum, maximum and final clinical laboratory evaluation will be analyzed using one-way ANOVA with treatment as the main effect.

For each treatment group, shift tables will be generated showing the number and percentage of subjects with low, normal, high and missing values at baseline and final observation based on the reference ranges provided by each laboratory.

The number and percentage of subjects in each treatment group who have values meeting predefined criteria for potentially clinically significant values ([Appendix D](#)) at any time after the first dose of study drug and no more than 20 weeks after the last dose of study drug will be summarized separately for hematology and chemistry variables.

8.1.6.3 Analysis of Vital Signs and Weight

Vital sign variables include pulse rate, systolic blood pressure, and diastolic blood pressure, body temperature, weight, and BMI. Pulse rate and blood pressure variables will include measurement in the supine position, measurement in the standing position and the orthostatic change (from supine to standing).

Change from baseline to each double-blind visit value and to the minimum, maximum and final double-blind value will be presented for each vital sign and weight variable and analyzed using one-way ANOVA with treatment as the main effect.

The number and percentage of subjects in each treatment group who have values meeting predefined criteria for potentially clinically significant values (definitions will be provided in the Statistical Analysis Plan) at any time after the first dose of study drug and no more than 20 weeks after the last dose of study drug will be summarized.

8.1.6.4 Analysis of ECG Variables

ECG variables include heart rate, PR, QRS, QT, and QTcF intervals. Change from baseline to final double-blind value will be presented for each ECG parameter and analyzed using one-way ANOVA with treatment as the main effect.

The number and percentage of subjects in each treatment group who have values meeting predefined criteria for potentially clinically significant values at any time after the first dose of study drug will be summarized.

8.1.6.5 Analysis of C-SSRS

Number and percentage of subjects in the following categories will be summarized for each treatment group by visit and for the entire study:

- Answered 'Yes' to each C-SSRS item
- Had suicidal ideation (defined as answering 'Yes' to one or more suicidal ideation items)

- Had suicidal ideation only (defined as answering 'Yes' to one or more suicidal ideation items and answering 'No' to all suicidal behavior items)
- Had suicidal behavior (defined as answering 'Yes' to one or more suicidal behavior items)
- Had suicidal ideation or behavior (defined as answering 'Yes' to one or more suicidal ideation or behavior items)

8.1.7 Pharmacokinetics

8.1.7.1 Tabulations and Summary Statistics

For the combined data of Cohort 1 and Cohort J1, serum concentrations of ABBV-8E12 and pharmacokinetic parameter values will be tabulated for each subject and each dose level, and summary statistics will be computed for each sampling time and each parameter by dose level. Also, for the serum concentration data of all subjects (Cohort 1, Cohort J1, and Cohort 2), summary statistics will be provided for each scheduled time of sampling with breakdown by dose level.

CSF concentration data after the fifth dose (for subjects in Cohort 1 and Cohort J1) and the final dose will be tabulated and summarized by dose level.

8.1.7.2 Model and Tests

Unless stated otherwise, hypothesis tests will be performed at significance level 0.050.

Change in Concentration with Repeated Dosing

The concentration data of the planned pre-infusion sampling times of Cohort 2 (Days 15, 29 and 85 plus Weeks 24 and 36) will be analyzed to investigate change in serum concentration over time. The data of Cohort 1 and Cohort J1 will also be included in this analysis except for Day 29. The logarithmic transformation will be used unless the data show that the logarithm has substantial non-symmetry (e.g., magnitude of skewness coefficient > 1.0) while untransformed concentration or another transformation has an approximately symmetric distribution. A MMRM analysis will be performed. The model

will have fixed effects for dose level, classification by time and the interaction of dose level and time. The subjects will be viewed as a random sample, and an appropriate structure will be selected for the covariance matrix of the observations from a subject. The concentration central value (back transformation of the estimate of the mean of the transformed data) versus time curves for the two dose levels will be plotted on the same graph.

Dose Proportionality

Analyses to address the issue of dose proportionality will be performed on the combined data of Cohort 1 and Cohort J1. An analysis will be performed on each of dose normalized C_{\max} and dose-normalized AUC for each of the first dose interval (2 weeks in length) and the dose interval beginning at Day 85 (4 weeks in length). An analysis will also be performed on dose-normalized C_{trough} at Week 16. The logarithmic transformation will be employed for C_{\max} and AUC and will likely be used for C_{trough} . An analysis of covariance (ANCOVA) will be performed for each exposure variable, with the greater emphasis on the dose interval that begins at Day 85. Subjects will be classified by dose level and region, and the initial model will contain an effect for the interaction of dose level and region. Body weight will be a covariate. Other variables such as age and sex that might explain some of the variability among subjects will be considered for inclusion as covariates. A necessary condition for such a variable to be included in the final model is that the regression coefficient be significant at level 0.100. The dependence among explanatory variable candidates will also be considered when selecting the final model. If the test statistic for interaction of dose level and region is not significant at level 0.100 for at least one of the three exposure variables for the dose interval beginning at Day 85, the effect for interaction will be removed from the model for all variables for both dose intervals. For each of the two dose intervals for each variable, the hypothesis of no difference between the dose level main effects will be tested (a composite assessment across the regions) within the framework of the final model. If the final model contains an effect for interaction of dose level and region and if the test statistic on interaction is

significant at level 0.100, the hypothesis of no difference between the dose levels will be tested for each region within the framework of the final model.

8.1.7.3 Missing Values and Model Violations

The possibility of bias from missing data of subjects who prematurely discontinue for reasons possibly related to study drug will be addressed.

In some cases of a missing individual concentration value, values of pharmacokinetic variables (C_{max} , AUC, etc.) will be determined without replacing missing individual concentration values, but simply using the available data. However, if a missing individual concentration value results in a value of a pharmacokinetic parameter that may be too low or too high to a meaningful degree, the value of the pharmacokinetic parameter will tentatively be considered missing. In this case, a value for the missing individual concentration may be imputed so that an appropriate value of the pharmacokinetic parameter can be included in the analysis. The imputed value will be obtained using appropriate methodology that takes into account the individual characteristics of the subject. Also, if the concentration value at the beginning or end of the dose interval is missing, a value must be imputed in order for a value of AUC to be determined.

Transformation of variables in order to avoid a meaningful degree of non-normality in the probability distributions is discussed in Section 8.1.7.2. If an adequate transformation is not found for a variable, then a non-parametric analysis may be performed.

8.1.7.4 Population Pharmacokinetic and Exposure-Response Analysis

Data from this study may be combined with data from other studies for the population pharmacokinetic and exposure-response analyses. Population pharmacokinetic and exposure-response analyses of only data from this study may not be conducted. The following general methodology will be used for the population pharmacokinetic and exposure-response analyses.

Population pharmacokinetic analyses will be performed using the actual sampling time relative to dosing. Pharmacokinetic models will be built using a non-linear mixed-effect modeling approach with the NONMEM software (version VII, or higher version). The structure of the starting pharmacokinetic model will be based on the pharmacokinetic analysis of data from previous studies and Cohort 1 and Cohort J1 of this study. Apparent CL and volume of distribution (V) of ABBV-8E12 will be the pharmacokinetic parameters of major interest in the NONMEM analyses. If necessary, other parameters may be fixed if useful in the analysis.

The evaluation criteria described below will be used to examine the performance of different models.

The objective function of the best model is significantly smaller than the alternative model(s).

The observed and predicted concentrations from the preferred model are more randomly distributed across the line of unity (a straight line with zero intercept and a slope of one) than the alternative model(s).

Visual inspection of model fits, standard errors of model parameters and change in inter-subject and intra-subject error.

Once an appropriate base pharmacokinetic model (including inter- and intra-subject error structure) is developed, empirical Bayesian estimates of individual model parameters will be calculated by the posterior conditional estimation technique using NONMEM. The relationship between these conditional estimates of CL and V values and potentially physiologically relevant or clinically meaningful covariates (such as subject age, sex, body weight, concomitant medications, laboratory markers of hepatic or renal function, etc.) will be explored using either stepwise forward selection method, or generalized additive method (GAM), or another suitable regression/smoothing method at a significance level of 0.050. After identification of all relevant covariates, a stepwise backward elimination of covariates from the full model will be employed to evaluate the

significance (at $P < 0.005$, corresponding to a decrease in objective function > 7.88 for one degree of freedom) of each covariate in the full model.

Linear or non-linear relationships of primary pharmacokinetic parameters with various covariates will be explored.

Relationships between exposure and clinical observations (primary efficacy variable) will be explored with Cohort 1, Cohort J1, and Cohort 2 data combined. Exposure-response relationships for secondary efficacy variables and/or some safety measures of interest may also be explored. Initially, the time-course of placebo response will be modeled. Subsequently the relationship between exposure (e.g., population pharmacokinetic model predicted average concentrations or AUC or trough concentrations of the individual model-predicted pharmacokinetic profiles, or some other appropriate measure of exposure) and drug effect will be explored after accounting for the time-course of placebo response. Several classes of models (e.g., linear, log-linear, exponential, E_{max} , sigmoid E_{max} , etc.) will be evaluated to characterize the exposure-response relationship based on the observed data.

Additional analyses will be performed if useful and appropriate.

The possibility of bias from missing data of subjects who prematurely discontinue due to an adverse event will be addressed.

8.1.8 Immunogenicity

The anti-drug antibody titers will be tabulated by dose level and summarized as appropriate.

Additional analyses will be performed if useful and appropriate.

8.1.9 Data Monitoring Committee (DMC)

This study will utilize a DMC consisting at least 2 external clinicians, at least 1 external statistician, and at least 1 external pharmacokineticist. The DMC will review unblinded

safety and efficacy data and make recommendations to AbbVie based on the totality of available trial data. An independent Statistical and Data Analysis Center (SDAC) and Exposure-Response Analysis Center (ERAC) will provide service to the DMC. Unblinded data will be kept by the SDAC and ERAC that will be conducting the analysis and preparing unblinded reports for the DMC and will not be released to the study team or study sites. The DMC will provide recommendations about continuing, modifying, or stopping the trial for safety or efficacy reasons. The DMC membership and responsibilities will be documented in the DMC charter. After each DMC meeting, the chair of the DMC will communicate its recommendations to the designated AbbVie Point of Contact, as described in the DMC charter. The AbbVie Representative will triage the recommendations to either the AbbVie Study Team if the recommendation can be implemented without unblinded data review or the AbbVie Internal Review Committee (IRC) if unblinded data review is required. The AbbVie IRC will consist of a group of senior individuals representing, at a minimum, the Therapeutic Area (TA), Pharmacovigilance and Patient Safety (PPS), Regulatory Affairs (RA), Clinical Pharmacology and Pharmacometrics (CPPM), and Data and Statistical Sciences (DSS), who are not directly involved in the conduct of this clinical trial. Members of IRC have technical depth to competently make decisions based on DMC recommendations to either (a) terminate the study or (b) implement significant unplanned protocol modifications.

8.1.10 Interim Analyses

Regular interim safety analyses and preplanned interim futility evaluation(s) will be performed in this study. Assessment of safety and efficacy data at interim(s) will be performed by the DMC.

Safety Interim Analyses

The DMC will evaluate the available unblinded safety data and communicate their recommendations to the AbbVie Point of Contact. The first three mandatory DMC reviews of unblinded safety data will take place after the 10th, 20th, and 30th subjects in Cohort 1 have been administered their second dose and results for the MRI scheduled at

approximately 2 weeks after their second dose are available. An additional mandatory DMC review for Japanese subjects will take place after the 9th subject enrolled in Japan (Cohort J1) has been administered their second dose and results for the Day 15 Safety labs and MRI performed within 2 weeks after their second dose, are available for comparison with previous DMC review results as Cohort J1 patients' safety assessment. The data set will consist of all of the available safety and pharmacokinetic data in the study, including the data of any subjects from Cohort 2 who have received at least one dose of study drug. Additional DMC reviews of available safety data will occur after a total of approximately 80, 130, 180, 240, and 330 subjects are randomized and every 6 months thereafter until the study has completed. Ad hoc meetings may occur as needed.

The DMC will communicate their recommendations to the AbbVie Contact (who is not involved in the conduct of the trial) regarding continuing, modifying or terminating the trial due to safety concerns in accordance with the DMC charter. Details of safety interim analyses will be specified in the DMC Charter.

Futility Interim Analyses

Preplanned futility interim analyses may be performed. The SDAC will be responsible for generating and providing unblinded statistical tables, figures, and listings to the DMC for the interim review for futility. The DMC will communicate their recommendations to stop the trial for futility or to continue the study without modification to the AbbVie Contact who will share it with the IRC only. The study will not be stopped because of positive results at the interim analyses and the α to be administratively spending at each interim analysis will be 0.00001. DMC recommendations will not be communicated to the study team, study investigators, or any parties outside of the Sponsor. To maintain the integrity of the trial, a specific data access plan with a strict firewall will be in place to protect the unblinded data and the details will be described in the DMC charter.

Details of futility interim analyses plan will be described in the DMC charter and the SAP.

8.2 Determination of Sample Size

Approximately 330 PSP subjects (110 subjects/group) will be enrolled and randomized to two ABBV-8E12 dose groups and the placebo group with 1:1:1 randomization ratio. This sample size has at least 90% power to detect an ABBV-8E12 effect size (vs. placebo) of 0.56 for the high dose and 0.28 effect size for the low dose on the PSPRS total score changes from baseline at Week 52 using the Bonferroni method to control for multiplicity of multiple comparisons between two doses and placebo at the two-sided 5% significance level. This sample size calculation was performed using East version 6.3.1 (Cytel).

In Japan, a total of 24 subjects (8 subjects/arm) randomized will have 80% probability to detect the consistent treatment effect among three regions (Japan, North America including US/Canada, and European countries including Australia assuming 7%, 54%, and 39% of the total 330 PSP subjects are randomized in three regions, respectively). This calculation is based on Method 2³¹ and assumes that the significance level for comparison of each ABBV-8E12 dose vs. placebo is two-sided 2.5% and the dropout rate is 25% in all regions.

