8.1.3 Efficacy Analyses

[figure not shown]
All efficacy analyses will be conducted on the intent-to-treat data set unless otherwise specified. Data collected more than 45 days after the last dose of the study drug will not be included in efficacy analyses. Unless otherwise specified, for all efficacy analyses, "baseline" refers to the last non-missing observation prior to the first dose of study drug and "final" refers to the last non-missing observation after the first dose of study drug and no more than 45 days after the last dose of study drug administration. Pairwise

comparisons between each ABBV-8E12 dose group and the placebo group will be performed with two-sided tests. Hochberg procedure²⁷ will be used for the efficacy analysis to handle multiplicity of comparisons between multiple ABBV-8E12 doses and placebo at the pre-specified significance level at the interim analysis. For the final analysis, a graphic approach³⁰ will be used to propagate alpha (α) among hypotheses testing and control overall family-wise error rate due to multiple comparisons for primary and key secondary efficacy endpoints for multiple ABBV-8E12 doses. The overall α for the final analysis is 0.04998 after adjusting for interim futility analyses. The α will be split equally between two dose groups to test the primary and key secondary endpoints at Week 52 within each dose level. The order of efficacy endpoints to be tested will be the same within each dose level (Table 9). The primary endpoint will be tested first followed by the secondary endpoints and α could be propagated between two doses and two families of hypotheses testing based on the graphic approach (Figure 3). In the graph, the arrows specify the α transfer paths. Once an endpoint is rejected (i.e., deemed significant) at its assigned significance level, its significance level will be transferred to subsequent endpoint(s) following the arrow(s). The numbers on the arrows denote the weights for transferring and (possibly) splitting the significance level. The overall type I error rate for this trial will be controlled at the two-sided 5% level. The detailed hypotheses testing procedure and the details of analyses methods will be pre-specified in the Statistical Analysis Plan (SAP) which will be finalized and signed off before the first futility interim analysis of this trial.

Table 9. Hypotheses Testing Order in the Graphical Testing Approach

Efficacy Endpoints Family	Ordered Efficacy Endpoints	Hypotheses	

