4.3 Sample Size

Approximately 330 PSP subjects (110 subjects/group) will be enrolled and randomized into two ABBV-8E12 dose groups and the placebo group with 1:1:1 randomization ratio. This sample size has ~90% power to detect an ABBV-8E12 effect size (vs. placebo) of 0.56 for the high dose and 0.28 effect size for the low dose on the PSPRS total score changes from baseline at Week 52 using the Bonferroni method to control for multiplicity due to multiple comparisons between two doses and placebo at the two-sided 5% significant level. A no data rate of 25% at Week 52 is assumed in this sample size calculation using East version 6.3.1 (Cytel).

In Japan, a total of 24 subjects (8 subjects/arm) randomized will have 80% probability to detect the consistent treatment effect among three regions (Japan, North America including US/Canada, and European countries including Australia assuming 7%, 54%, and 39% of the total 330 PSP subjects are randomized in three regions, respectively). This calculation is based on Method 2¹ and assumes that the significance level for comparison of each ABBV-8E12 dose vs. placebo is two-sided 2.5% and the dropout rate is 25% in all regions.

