Two pre-planned interim efficacy analyses for futility will be performed. The DMC will communicate their recommendations to AbbVie Contact who will share recommendations to the Sponsor. The DMC will make recommendation to the Sponsor to stop the trial for futility or to continue the study without modification. The study will not be stopped because of positive results at the interim futility analyses and administrative α spending at each interim analysis will be 0.00001. Futility interim analyses will be conducted on PSPRS total score changes from baseline.

Mixed Model Repeated Measure (MMRM) analysis on PSPRS total score change from the baseline up to Week 52 using observed data will be conducted in the futility interim analyses.

Rules for Interim Futility Analyses

A simulation study was conducted to determine the timing and decision making thresholds for futility interim analyses (see details of the simulation report in the DMC Charter).

The timing of futility interim analysis was determined based on the need to have sufficient information available to make a decision with reasonable confidence. Two futility interim analyses are planned for this trial. The first futility interim is planned to occur when approximately 60 subjects (20 subjects/group) have completed 52 Week visit; the second futility interim is planned to occur when approximately 120 subjects (40 subjects/group) have completed 52 Week visit (see projected timing on Table 1 in simulation report in the DMC Charter).

At both futility interim analyses, if observed effect sizes at Week 52 for both doses are below the threshold, the DMC will make the recommendation to terminate the study due to futility.

Details of interim futility analyses plan will be described in the DMC charter for this study.

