10.6 Handling of Multiplicity

Pairwise comparisons between each ABBV-8E12 dose group and the placebo group will be performed with two-sided tests. Hochberg procedure² will be used for the efficacy analysis to handle multiplicity of comparisons between multiple ABBV-8E12 doses and placebo at the pre-specified significance level at the interim analysis ($\alpha = 0.00001$ at each futility interim analysis), which is described in the DMC Charter.

[figure not shown]
For the final analysis, a graphic approach³ will be used to control overall family wise error rate due to multiple comparisons for primary and key secondary efficacy endpoints for multiple ABBV-8E12 doses. The overall α for the final analysis is 0.04998 after accounting for α spending at interim futility analyses. This α will be split equally between two dose groups to test the efficacy endpoints in the primary and key secondary families within each dose level at Week 52. The order of efficacy endpoints to be tested is PSPRS

total score change at Week 52, UPDRS-II score change at Week 52, CGI-C score at Week 52, midbrain atrophy measured by volumetric MRI change from baseline at Week 52, SEADL score change at Week 52 (Table 3). The primary endpoint will be tested first followed by the secondary endpoints and α could be propagated between two doses and two families of hypotheses testing based on the graphic approach (Figure 2). In the graph, the arrows specify the α transfer paths. Once an endpoint is rejected (i.e., deemed significant) at its assigned significance level, its significance level will be transferred to subsequent endpoint(s) following the arrow(s). If more than one arrow originates from an endpoint, the significance level for this endpoint (once rejected) will be split between multiple subsequent endpoints following the arrows. The numbers on the arrows denote the weights for transferring and (possibly) splitting significance levels. Specifically, the weight 1 denotes 100% transfer of significance level. The number underneath of each hypothesis is the original weight for α splitting assigned to the hypothesis. The overall type I error rate for this trial will be controlled at the two-sided 5% level. Nominal P values and multiplicity adjusted P values for all variables listed in Table 3 will be presented in a table.

Table 3. Hypotheses Testing Order in The Graphical Testing Approach

Efficacy Endpoints Family	Ordered Efficacy Endpoints	Hypotheses	

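### The single 90% power figure does not say which power it is; it fits the high dose or at least one dose, while Bonferroni power for the low dose is about 33%

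*Protocol*

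**What the plan says.** Protocol 8.2 sets the size of the trial: "Approximately 330 PSP subjects (110 subjects/group) will be enrolled and randomized to two ABBV-8E12 dose groups and the placebo group", allocated 1:1:1. It claims, as a minimum, "90% power to detect an ABBV-8E12 effect size (vs. placebo) of 0.56 for the high dose and 0.28 effect size for the low dose". The endpoint is PSPRS change at Week 52, with Bonferroni across the two dose comparisons at an overall two-sided 5% level.

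SAP 4.3 makes the same claim with a softer figure: "This sample size has ~90% power to detect an ABBV-8E12 effect size (vs. placebo) of 0.56 for the high dose and 0.28 effect size", the second effect being that of the low dose. It adds an assumption that the protocol paragraph lacks: "A no data rate of 25% at Week 52 is assumed in this sample size calculation". In Protocol 8.2 a 25% dropout rate appears only in the separate Japan consistency calculation.

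Two other parts of the plan bear on how the figure should be read:

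- **Testing.** Protocol 8.1.3 says: "The α will be split equally between two dose groups to test the primary and key secondary endpoints at Week 52". The high-dose and low-dose PSPRS comparisons (H11 and H21) both sit in the primary family. SAP 10.6 adds that "α could be propagated between two doses and two families of hypotheses testing based on the graphic approach".
- **Futility.** Under SAP 4.4 the recommendation to stop for futility is made only "if observed effect sizes at Week 52 for both doses are below the threshold".

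**The concern.** One power figure is attached to two effect sizes, one half the other, at equal group sizes and equal alpha. It cannot be the power of each comparison, and neither section says what it is instead. As worded, the sentence covers detecting 0.28 at the low dose, and no other sentence in either document gives a power for that comparison.

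H21 is a primary hypothesis with its own half of the alpha, so its power affects how the result will be read. If 2000 mg misses significance, a reader who takes the 90% at face value would see strong evidence against an effect of 0.28. If the true power is a third to a half, a miss says little. That should be on record before results are known, because afterwards it would look like an excuse.

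**Working it through.** **Inputs**

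- 110 randomized per group, 1:1:1 (Protocol 8.2, SAP 4.3).
- Standardized effects 0.56 (4000 mg) and 0.28 (2000 mg) (both sections).
- Bonferroni at two-sided 5% overall, so 2.5% per dose and z = 2.2414. The Japan paragraph also states 2.5% per dose.
- 25% without Week 52 data (SAP 4.3): 110 × 0.75 = 82.5 evaluable per group.
- Final-analysis alpha 0.04998, or 0.02499 per dose (SAP 10.6); used only for the recycling check.

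**Power per dose:** Φ(d·√(n/2) − z), with √(82.5/2) = 6.4226.

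- High dose: 0.56 × 6.4226 = 3.597; 3.597 − 2.241 = 1.355; power **91.2%** (90.8% with a t-test).
- Low dose: 0.28 × 6.4226 = 1.798; 1.798 − 2.241 = −0.443; power **32.9%** (32.4% with a t-test).

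**Joint power.** The two statistics share the placebo group, so with equal groups their correlation is 0.5. From the bivariate normal:

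- Both doses: **32.3%**.
- At least one dose: 91.2 + 32.9 − 32.3 = **91.8%**.

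The plan's figure therefore reproduces on two of the four readings.

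**Recycling.** The graph's weights are in a figure not reproduced in the text available for this review, so a range is used. Let w be the share of the high-dose alpha that passes directly to the low-dose primary test once the high dose is rejected, and a = 0.02499. Low-dose power is then

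P(Z_L > z_a) + P(Z_H > z_a, Z_L > z_{a(1+w)}) − P(Z_H > z_a, Z_L > z_a).

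| w (assumed) | Low-dose power, 82.5 per group |
|---|---|
| 0 (Bonferroni) | 32.9% |
| 0.25 | 36.0% |
| 0.50 | 38.7% |
| 0.75 | 41.0% |
| 1 | 43.1% |

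A simulation of 2 million trials with full recycling also gives 43.1%.

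**Missing data.** Using 82.5 counts only subjects with Week 52 data. The MMRM also uses Weeks 12, 24 and 36, so 82.5 and 110 per group bracket the effective size. At 110 per group:

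- High dose: 97.2%.
- Low dose: 43.5% under Bonferroni and 54.5% with full recycling.

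**Required size for 90% power:** n = 2·((2.2414 + 1.2816)/d)².

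- d = 0.56: 80 evaluable per group; 80/0.75 = 107 randomized, close to the planned 110.
- d = 0.28: 317 evaluable per group; 317/0.75 = 423 randomized, against 110 planned.

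**The case against.** The strongest reply is that this is a gap in labelling. One figure for a pair of unequal effects at equal n reads naturally as power for the configuration, meaning at least one dose. The futility rule, which requires both doses to miss, follows the same logic. On that reading the number is right, and N is sound.

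Much of this stands. N is not in error, and at-least-one power fits the futility rule. But neither sample-size section names that reading, and high-dose power fits the number almost equally well (91.2% against 91.8%). A reader has to redo the calculation to rule out the reading that the words suggest.

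A second reply is that 33% is the least favourable case, because plain Bonferroni is not the final test and a completers-only count ignores partial MMRM data. It is fair that the supported range runs from about 33% to about 54%, and that the recycling values rest on assumed weights. But Bonferroni with 25% no data is the basis that the SAP itself gives for its figure, and the top of the range is still far below 90%.

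On the omitted 25%: without dropout the high-dose power is 97.2%, so the protocol's claim of at least 90% remains true for that dose. What is lost is the ability to see from the protocol alone how 110 per group was reached.

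**Conclusion.** The concern holds. The stated power is correct for the high dose alone or for at least one dose. It overstates low-dose power by about 57 points on the plan's own Bonferroni basis (90 − 32.9), and by about 35 points in the most favourable case examined (90 − 54.5).

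With 25% no data, a true low-dose effect of 0.28 would miss significance in about 67% of trials under Bonferroni and about 57% with full recycling. With no missing data and full recycling the miss rate is about 46%.

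These figures rest on normal approximations, equal evaluable group sizes and assumed recycling weights; the t-test and simulation checks agree. Type I error control, the analysis and the sample size are unaffected. It should be fixed because the sentence concerns a primary hypothesis.

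**What to change.** In Protocol 8.2 and SAP 4.3, name the type of power and give the low-dose figure separately. For example:

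*With 110 subjects per group, 25% without Week 52 data and Bonferroni two-sided alpha of 0.025 per dose, power is about 91% for the high dose at an effect size of 0.56 and about 92% for at least one dose. For the low dose at 0.28, Bonferroni power is about 33%; it may be higher under the graphical procedure, depending on its weights.*

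The sponsor holds the graph and could replace the last clause with a value computed from the actual weights. The example also brings the 25% no-data rate into Protocol 8.2.

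The cost is one or two sentences in each section and a less favourable low-dose figure on view. No patients are added, and sample size, alpha and analysis stay as they are.
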